## **8.2. Statistical and Analytical Plans**

For the analysis of efficacy, the intention-to-treat analysis will be used, which will include all patients who were treated with at least one dose of FK. Categorical variables are reported using frequency and percentages while continuous variables are expressed as medians with ranges. A chi-square statistic will be used to evaluate the null hypothesis of no difference between the standard dose group and genotype based group within the FK target range on day 3 after transplantation. Continuous data will be compared using the Mann-Whitney U test. The time to reach target FK range will be estimated with Kaplan-Meier survival analysis and compared between the groups using log-rank test. To estimate the overall effect of CYP3A5 genotype on the outcome variables of FK daily dose, FK trough concentration and dose-adjusted FK level (a measure of apparent oral clearance), a mixed between-within subjects analysis of variance will be used. This analysis will also be used to estimate the overall effect of dosing approach on renal function. All data are analysed using R Core Team (2017). A p-value < 0.05 is considered statistically significant.

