## 1. BACKGROUND AND RATIONALE

Tacrolimus (FK) remains the cornerstone of maintenance immunosuppressants after renal transplantation. However, it is characterised by narrow therapeutic index and large inter-individual variability in its pharmacokinetics, particularly in the dose required to reach target trough blood concentrations. Among several factors investigated for their possible influence on tacrolimus pharmacokinetics, polymorphisms in genes coding for biotransformation enzymes (cytochrome P450 (CYP) isoenzymes 3A4 and 3A5) have received much attention. Exposure to FK correlates with the cytochrome P450 (CYP) 3A4 and CYP3A5 which are polymorphically expressed. This is in part explained by the presence of single-nucleotide polymorphisms (SNPs) in the CYP3A5 and CYP3A4 genes.

A SNP at position 6986 of the CYP3A5 gene (rs776746; 6986A>G; designated as CYP3A5 \*3) results in a splicing defect that causes non-functional CYP3A5 protein (Birdwell KA et al, 2015). In retrospective studies, it has been demonstrated that whole-blood tacrolimus trough concentration and tacrolimus dose requirements are closely associated with CYP3A5 polymorphism: patients carrying at least one CYP3A5\*1 allele have a lower tacrolimus concentration/dose ratio than that in nonexpressers (CYP3A5\*3/\*3) among kidney, liver, lung, and heart transplant recipients. In a cohort of kidney transplant recipients, a 2.3-fold difference was observed in the daily dose required to maintain target FK trough concentration in CYP3A5\*3\*3 and CYP3A5\*1\*1 patients (Haufroid V et al, 2004). Moreover, a significant delay in reaching target FK trough concentration and a shorter time to acute rejection were observed during the first 2 weeks after kidney transplantation in CYP3A5 expressers (MacPhee et al, 2004).

To date, renal transplant (RTx) recipients receive standard weight-based dosing of FK and therapeutic drug monitoring is employed for subsequent dose adjustment to ensure target FK concentration is attained. However, the current weight-based dosing strategies to guide the initial FK dosing have been poorly predictive of the actual FK dose required to attain therapeutic FK level (Loh PT et al, 2008). With the increased possibility of sub-therapeutic FK level during the early phase post renal transplantation, it puts them at a higher risk of developing acute rejection.

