There has been increasing evidence to suggest the implementation of pre-transplantation genotyping to guide the initial FK dose to achieve target FK concentrations as quickly as possible (Chen SY et al, 2013; Shuker N et al, 2016; Pallen N et al, 2016; Zhang J et al. 2010). Min SI et al revealed that in RTx patients who received equal doses of FK, the CYP3A5 expressers (\*1\*1 and \*1\*3 genotypes) had lower FK level and a higher incidence of acute cellular mediated rejection than the CYP3A5 non-expressers (CYP35 \*3\*3 genotype). Furthermore, multivariate analysis identified CYP3A5 expression as an independent risk factor for cellular mediated rejection (odds ratio 2.79; p=0.043) (Min SI et al, 2010). On the contrary, there are a few studies that report contradictory results of genotype-guided FK dosing as being useful in attainment of target therapeutic levels. A randomized controlled trial by Thervet et al demonstrated that while target FK levels were achieved earlier in incident kidney transplant recipients whose tacrolimus dose was chosen based on CYP3A5 genotype versus a control group that started tacrolimus based on standard weight-based dosing (Thervet et al, 2010), no

differences were seen in patient survival, nephrotoxicity, or acute rejection over the three-month follow-up. A key limitation of the study was tacrolimus was introduced only 7 days after transplantation in the CYP3A5 genotype-based dosing group while it was started at time of transplantation in the weight-based dosing group. Prevalence of CYP3A5 genotypes is also different in various ethnicities. For example, the Caucasian proportions of CYP3A5 expressers (CYP3A5 \*1\*1 and \*1\*3) were 18% while in our local multiethnic population, CYP3A5 expressers make up 51% of the renal transplant population (Loh PT et al, 2008).

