## **2. HYPOTHESIS AND OBJECTIVES**

We hypothesise that the adaptation of CYP3A5 genotype-based FK dosing will lead to earlier FK target achievement and consequently, better clinical outcome after RTx.

This study aims to shed light on the possible impact of CYP3A genotype-based FK dosing on FK target achievement and clinical outcome after RTx in a multi-ethnic population where current evidence is lacking. This data would be helpful to the physicians so that by knowing the genotype of the patient before undergoing transplantation, they would be able to decide on the starting dose of FK so as to avoid low trough levels and risk of acute rejection or high trough levels and risk of nephrotoxicity.

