#### Rationale for Selection of Dose:

Patients will be assigned to receive an initial CYP3A5 genotype-based tacrolimus (FK) dose of

0.15 mg/kg/day (CYP3A5 non-expresser) or 0.20 mg/kg/day (CYP3A5 expresser).

The current Clinical Pharmacogenetics Implementation Consortium (CPIC) Guidelines for CYP3A5 genotype and Tacrolimus Dosing recommend that

- CYP3A5 expressers e.g. carriers of at least one CYP3A5\*1 allele) receive 1.5 – 2 times the standard starting dose of tacrolimus
- CYP3A5 non-expressers e.g. carriers of CYP3A5 \*3/\*3 receive 0.075 mg/kg/dose twice daily

At SGH, the standard starting dose of Prograf® is 0.15 mg/kg/day. Based on the CPIC guidelines, CYP3A5 expressers will receive an initial dose of 0.20 mg/kg/day (rounded down). Subsequent drug doses will be adjusted based on drug levels.

All the proposed initial doses of tacrolimus are within the local approved package insert for Prograf®, which recommends an initial dose of 0.15 to 0.30 mg/kg/day for adult kidney transplant patients.

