#### FK measurement and genotyping

FK trough level will be determined in whole blood using liquid chromatography and tandem mass spectrometry (LC-MS/MS) method.

Two venous blood samples (3 mL each) for CYP3A5 genotyping will be obtained from all study participants. The subjects' blood samples will be de-identified and sent to the molecular laboratory in Tan Tock Seng Hospital, Singapore, which is offering CYP3A5 genotyping as a clinical service. Briefly, the genomic DNA is extracted from ethylenediaminetetraacetic acid anticoagulated whole blood samples using a QIAamp DNA mini kit (Qiagen, Hilden,

Germany), according to the manufacturer's protocol. Real-time polymerase chain reaction (RT-PCR) is then performed with a 7900 Real-Time PCR System. RT-PCR consisted of a denaturation step at 95°C for 10 minutes, then 50 cycles of 15 seconds at 92°C and 1 minute 30 seconds at 69°C. CYP3A5 6986A>G (rs776746) allelic discrimination is undertaken with a Custom TaqMan® SNP Genotyping Assay and VIC and FAM reporter dyes. No phenotyping will be done for CYP3A5. Once the blood sample has been genotyped, it will be destroyed as agreed upon by the molecular laboratory at Tan Tock Seng Hospital. The genotyping results will then be re-identified by the PI or co-investigators. The genotyping result will not be communicated to the subjects.

The blood sample will be destroyed immediately after sample analysis.

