#### Clinical assessment

Demographic and baseline data included the age, gender, race, weight and height of the recipient, cold ischemia time, the flow panel-reactive antibody value before transplantation and at its peak, the CMV serostatus of the donor and recipient. Laboratory data — including hemoglobin level, white-cell and platelet counts, FK trough level, liver function panel, serum creatinine level and estimated glomerular filtration rate — are measured at baseline, days 0 through 7, 14±3, 30±3, 60±3 and 90±3.

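### The day-3 in-range and time-to-target comparisons of two non-randomised cohorts are fixed as unadjusted tests, although CYP3A5 genotype is planned for every participant

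*Protocol*

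**What the plan says.** Section 8.2 names a test for each of the two comparisons. For day-3 status: "A chi-square statistic will be used to evaluate the null hypothesis of no difference between the standard dose group and genotype based group". For time to target range, Kaplan-Meier curves will be "compared between the groups using log-rank test". Neither has a stratum, a covariate or matching.

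The groups are not randomised. Under Section 4.2 and the Treatment/dosing part of Section 5, controls were transplanted from January 2016 to December 2020 and must still be under follow-up. The genotype-dosed patients are transplanted from January 2021 to January 2023. Sections 4.1 and 8.1 explain that randomisation was judged unrealistic.

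On genotype, the Background states that "whole-blood tacrolimus trough concentration and tacrolimus dose requirements are closely associated with CYP3A5 polymorphism" and that "Prevalence of CYP3A5 genotypes is also different in various ethnicities"; it puts local expresser prevalence at 51%. Section 5 says "Two venous blood samples (3 mL each) for CYP3A5 genotyping will be obtained from all study participants". Race and age are also recorded: "Demographic and baseline data included the age, gender, race, weight and height of the recipient, cold ischemia time".

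In Section 8.2 genotype enters only a mixed analysis of variance for daily dose, trough and dose-adjusted level. The same method is used for the effect of dosing approach on renal function. Neither use adjusts the day-3 or the time-to-target comparison.

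**The concern.** These two comparisons carry the study's hypothesis that "the adaptation of CYP3A5 genotype-based FK dosing will lead to earlier FK target achievement". In a comparison of successive cohorts, a crude difference mixes the effect of the dosing policy with any difference in who was treated. The protocol itself names the patient factor most likely to matter for trough level and plans to measure it, then leaves it out of the two tests where it matters most.

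A second reason needs no imbalance. The protocol states: "At SGH, the standard starting dose of Prograf® is 0.15 mg/kg/day". Non-expressers in the genotype arm start at that same stated dose; only expressers start at a different one (0.20 mg/kg/day). The starting-dose contrast therefore exists in about half the patients. A pooled test dilutes it and gives no separate view of non-expressers, in whom a difference between cohorts would point to period or selection effects.

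Sections 4.1 and 8.1 say a trend seen here would lead to a larger multi-centre study, so a misread contrast would carry forward into that design.

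**Working it through.** The protocol gives no in-range rates, effect size, power or split between cohorts, so there is no stated figure to reproduce. The calculations are illustrations.

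**Inputs from the protocol:** total 100 (Section 8.1), expresser prevalence 51% (Section 1), significance level 0.05 (Section 8.2).

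**Assumptions:**
- cohort splits of 50/50, 60/40 and 80/20 (control/genotype arm);
- in-range rates, expressers against non-expressers, of 15%/45%, 20%/40% or 25%/35%;
- expresser shares differing between cohorts by 0, 10, 20 or 30 points.

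**Step 1. Shift with no dosing effect.** Shift = (gap in in-range rate by genotype) × (difference in expresser share). With 15%/45% and shares of 40% and 60%: 30 × 0.20 = 6 points. With shares of 35% and 65%: 30 × 0.30 = 9 points.

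**Step 2. Chi-square error by hand, 50 per cohort, 15%/45%.** At shares 40/60 the in-range rates are 0.4×0.15 + 0.6×0.45 = 0.33 and 0.6×0.15 + 0.4×0.45 = 0.27. The pooled rate is 0.30.
- Null SE = √(0.30×0.70×2/50) = 0.0917.
- Actual SE = √(0.33×0.67/50 + 0.27×0.73/50) = 0.0915.
- Rejection = Φ[(0.06 − 1.96×0.0917)/0.0915] + Φ[(−0.06 − 1.96×0.0917)/0.0915] = 0.095 + 0.004 ≈ 0.10.

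The same steps at shares 35/65 give 0.163 + 0.002 ≈ 0.165.

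**Step 3. Simulation, 400,000 runs per cell, no dosing effect.** The ranges cover both directions of imbalance and the three splits.

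| Assumed in-range rates | Imbalance | Crude chi-square | Mantel-Haenszel |
|---|---|---|---|
| 15%/45% | 20 points | 0.070-0.103 | about 0.05 |
| 15%/45% | 30 points | 0.105-0.168 | about 0.05 |
| 20%/40% | 20-30 points | 0.056-0.102 | about 0.05 |
| 15%/45% | 10 points | 0.053-0.064 | about 0.05 |
| 25%/35% | any of these | 0.049-0.064 | about 0.05 |
| any of these | none | about 0.05 | about 0.05 |

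**Step 4. How often a gap arises by chance.** If both cohorts come from one 51%-expresser population, the SD of the difference in share is √[0.51×0.49×(1/n₁ + 1/n₂)]: 10.0 points at 50/50 and 12.5 at 80/20. Exact probabilities of a gap of at least 20 points are 0.057 and 0.122; of at least 30 points, 0.0035 and 0.018. Given a realised gap of at least 20 points and rates of 15%/45%, the crude test rejects a true null in about 9% to 10% of studies and Mantel-Haenszel in about 5%. With 20%/40% the crude figure is about 7% to 8%.

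**Step 5. A real effect confined to expressers** (15% to 45%; non-expressers 45% in both cohorts; 50/50). The true pooled difference is 0.5 × 30 = 15 points.
- Shares 40/60: crude difference 0.45 − 0.33 = 12 points; rejection 0.24 crude, 0.32 Mantel-Haenszel.
- Shares 60/40: crude difference 0.45 − 0.27 = 18 points; rejection 0.47 crude, 0.34 Mantel-Haenszel.

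At 80/20 and shares 40/60, the pooled expresser share is 0.8×0.4 + 0.2×0.6 = 0.44, so the true difference is 0.44 × 30 = 13.2 points. Standardising stratum-specific differences recovers 13.2; crude gives 12.0; a main-effects logistic model tends to 17.3.

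**Step 6. Log-rank, 20,000 runs,** five daily looks on days 3 to 7, no dosing effect, the assumed rates applied each day, imbalances of 20 to 30 points. The crude test rejects in about 8% to 33% for the two stronger covariates and 6% to 9% for the weak one. It rejects in about 5% with no imbalance. The stratified test rejects in 5% to 6% throughout.

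**The case against.** The strongest case against has six parts.

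- **Adjusted analyses may sit in an unseen SAP.** Possible. But the protocol names the crude tests for these endpoints, so they are fixed and not merely left open.
- **Nothing shows that expresser share differs between the cohorts.** Correct. Both come from one centre under the same criteria, and the ethnicity statement contrasts populations, not periods. If both share one expresser prevalence, the crude tests hold 5% averaged over all possible samples. What remains is the reading of the one pair of cohorts actually obtained: when a large gap occurs, the crude test is too liberal and the stratified one is not.
- **Genotype may not predict falling within a two-sided window.** This stands. The stated window for the genotype arm is 10 to 15 ng/mL; expressers could miss low and non-expressers high, with similar in-range rates. The weak-covariate rows show how little would then change.
- **The log-rank figures assume constant daily rates,** whereas the Endpoints text allows dose changes after the day-3 level. They are best read as upper illustrations.
- **Calendar period and control selection are the larger threats.** Perhaps so. With 50 per cohort, expressers at 20% and non-expressers at 50%, an assumed 10-point drift gives either test about 18% rejections.
- **Control genotype may not exist.** Section 5 promises it for all participants, yet Section 11.1 describes consent only at a visit before transplant. This affects feasibility and calls for a stated alternative.

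None of these removes the case for stratifying, which also rests on the stated starting dose differing from the standard only in expressers.

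**Conclusion.** The concern holds. Section 8.2 fixes unadjusted tests for two comparisons of non-randomised cohorts and leaves unused the covariate the protocol itself identifies and plans to collect. The size of any bias cannot be derived from the protocol. Under the stronger assumed covariates and a 20 to 30 point imbalance, chi-square error is about 6% to 17%; under weak or balanced conditions it is 5% to 6%. In the worked example with a real effect at 50/50, the crude difference is off by 3 points in either direction. Confidence is medium, because the in-range rates, imbalances and cohort split are all assumed. The change should be made before analysis, but stratification will not turn the historical comparison into an unbiased one.

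**What to change.** Keep the chi-square and log-rank tests and add the following to Section 8.2.

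1. For day 3, make an expresser-stratified comparison the one to interpret: a Mantel-Haenszel test, with a risk difference and 95% CI standardised from the stratum-specific differences to the pooled expresser distribution. Do not use a main-effects-only model as the main estimate.
2. Use a small-sample interval, for example adding one success and one failure to each cohort-by-stratum cell. In the illustrations this covered 0.952 to 0.969, against 0.88 to 0.92 for the Wald interval at 80/20.
3. Report the difference within each expresser stratum.
4. Place an expresser-stratified log-rank test beside the unadjusted one.
5. If control genotype cannot be obtained, adjust for race (two pre-specified groups) and age, and state that genotype confounding remains.
6. State that adjustment cannot remove calendar-period effects or the selection of controls still under follow-up.

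**Cost:** a paragraph and a few lines of code; control genotyping may need sampling and consent. In the illustrations the SE of the standardised difference runs from about 6% smaller to 20% larger than crude (0.133 against 0.111 at 80/20 with a 30-point imbalance). The interval within expressers is wide, roughly ±20 to ±33 points. Where imbalance happens to favour the new arm, the stratified test rejects less often than the crude one.

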#### Endpoints

The primary endpoint of the study is the proportion of patients within the desired FK trough level at first steady state e.g. morning of day 3 after five unaltered FK doses and the proportion of patients within target FK levels on day 7 post initiation of FK. The FK trough level is defined as the whole blood concentration 12 h  $\pm$  15 min after the previous dose taken the night before at 8pm. Thereafter, the clinicians can change the FK dose based on the measured FK

level and/or the clinical situation of the individual patient according to routine transplant immunosuppression protocol. For the genotyping arm, the pre-specified FK target range will be 10 – 15 ng/mL in the first 1 week after transplantation and subsequently adjusted based on routine transplant immunosuppression protocol.

Secondary pharmacokinetic endpoints include

- Proportion of patients within target FK levels on day 7 post renal transplant
- Average FK level during the first 1 weeks after transplantation
- Average daily dose of FK the first 90 days post transplantation [days 3, 7, 14±3, 30±3, 60±3, 90±3 days post transplantation]
- Average concentration-to-dose ratio of FK during the first 90 days post transplantation [days 3, 7, 14±3, 30±3, 60±3, 90±3 days post transplantation]
- Time to reach the first target FK range
- Number of FK dose adjustments required to reach the target FK level
- Number of markedly sub-therapeutic FK level (defined as <4 ng/mL) and markedly supra-therapeutic FK level (defined as > 20 ng/mL)

Secondary clinical endpoints include

- Incidence of biopsy-proven acute rejection (BPAR), with histologic characteristics described accordingly to the Banff criteria [Banff 1997 scoring system with 2007 modifications] and/or clinically presumed acute rejection
- Incidence of graft loss (defined as failure to discontinue dialysis or if patient undergoes graft nephrectomy)
- Renal function at month 3 after transplantation. Estimated GFR (eGFR) will be calculated using CKDEPI equation. [Time Frame: at day 7, 14, 30±3, 60±3 and 90±3 days after transplantation ]

All patients will be followed for at least 3 months after transplantation, or until graft loss occurs (defined as death with a functioning transplant, return to dialysis or re-transplantation), whichever occurs earlier.

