#### Withdrawal from study

Subjects may withdraw voluntarily from participation in the study at any time.

Possible reasons for discontinuation from the study include

- Switched out from tacrolimus to other immunosuppressants
- No longer on triple immunosuppressants either due to intolerance or infection-related complications
- Graft failure or death

If voluntary withdrawal occurs, the subject will be asked to continue scheduled evaluations, complete an end of study evaluation, and be given appropriate care under medical supervision until the symptoms of any adverse event resolve or the subject's condition becomes stable.

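### Renal function at month 3 is tested by an ANOVA effect averaged over days 7 to 90, in a model that handles incomplete series poorly

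*Protocol*

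**What the plan says.** Protocol section 8.2 uses one model for two purposes.

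- **Tacrolimus variables, factor CYP3A5 genotype:** "To estimate the overall effect of CYP3A5 genotype on the outcome variables of FK daily dose, FK trough concentration and dose-adjusted FK level", "a mixed between-within subjects analysis of variance will be used".
- **Renal function, factor dosing approach:** "This analysis will also be used to estimate the overall effect of dosing approach on renal function". No time point is named.

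The Endpoints part of section 5 gives the renal endpoint as "Renal function at month 3 after transplantation" and attaches five visits to it: "Time Frame: at day 7, 14, 30±3, 60±3 and 90±3 days after transplantation". Dose and concentration-to-dose ratio have six: "days 3, 7, 14±3, 30±3, 60±3, 90±3 days post transplantation".

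Section 8.2 defines the efficacy set as everyone who received at least one tacrolimus dose. It also gives a general rule for continuous data: Mann-Whitney tests, and "continuous variables are expressed as medians with ranges". Section 5 ends follow-up at graft loss, including death, and its reasons for discontinuation include "Switched out from tacrolimus to other immunosuppressants".

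**The concern.** Two things are at stake.

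First, the renal endpoint is a value at one time, but the only analysis section 8.2 names for renal function estimates an effect pooled over three months. The two can disagree. Faster early recovery in one group could be reported as a renal benefit at month 3 that does not exist, and a real month-3 difference could be diluted until it is missed.

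Second, a between-within ANOVA is built for patients with a value at every visit. The protocol expects some patients to stop early, for reasons that may be related to outcome. The model then either departs from the stated analysis set or loses its clean separation of between-patient and within-patient variation.

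**Working it through.** The protocol gives no figure to reproduce here: section 8.1 sets 100 subjects without an effect size, SD, power or split between groups. Assumptions are marked as such.

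**1. Overall effect against month 3.** With complete data, the overall group effect is the mean of the visit-specific differences over the five eGFR visits (section 5, Endpoints).

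- Early difference only (illustrative): (10 + 5 + 0 + 0 + 0)/5 = 3 mL/min overall, and 0 at month 3.
- Difference δ at month 3 only: δ/5.

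**2. What this does to the test.** Assume 50 per group, equal SD at each visit, correlation 0.7 to the power of the lag in visits, and two-sided 5%.

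- Variance of a patient's five-visit mean, in SD² units: [5 + 2(4×0.7 + 3×0.49 + 2×0.343 + 0.2401)]/25 = 15.39/25 = 0.616, so the SD is 0.785.
- Effect of 0.6 SD at month 3 only: the overall effect is 0.12 SD, and z = (0.12/0.785)×√(50/2) = 0.76, so power is about 12%. Simulation with 3,000 runs gives 12% for the overall test and 83% for a month-3 Mann-Whitney test.
- Early effect of 0.6, 0.6, 0.3, 0, 0 SD: the overall effect is 0.30 SD, and z = (0.30/0.785)×5 = 1.91, so rejection is about 48%. Simulation gives 48% for the overall test and about 5% for the month-3 test.

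**3. Incomplete series, if the model is run on complete cases.** With gaps independent between visits at an assumed rate m, the complete share is (1 − m)^visits.

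| Assumed missing per visit | Six tacrolimus visits | Five eGFR visits |
|---|---|---|
| 2% | 0.98⁶ = 89% | 0.98⁵ = 90% |
| 5% | 0.95⁶ = 74% | 0.95⁵ = 77% |
| 10% | 0.90⁶ = 53% | 0.90⁵ = 59% |

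Independence is the pessimistic case. If the same 5% of patients accounted for every gap, 95% would be complete.

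**4. Incomplete series, if the routine keeps the patients.** Section 8.2 names R but no function. Base R's aov with an error stratum was run on 20 simulated patients with five visits, then again with the last value removed for three of them. The patients stayed in: within-patient residual degrees of freedom fell only from 72 to 69. But R warned that the error model was singular, and time and group-by-time terms appeared in the between-patient stratum, whose residual degrees of freedom fell from 18 to 16.

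**5. Distribution.** With 50 per group, the between-group type I error was 4.8% to 4.9% for lognormal data, so skewness does little harm to that test. The group-by-time test without a sphericity correction ran at about 6.5% to 6.7%. For an assumed 1.3-fold difference, a simple two-group comparison had power of 74% on the raw scale against 78% on the log scale at a CV of 50%, and 47% against 54% at a CV of 70%.

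**The case against.** The strongest reply is that the renal endpoint lists five visits, so a repeated-measures analysis matches its time frame. A between-within ANOVA ordinarily contains a group-by-time term, and the general Mann-Whitney rule could cover eGFR at month 3. A reader might infer that month-3 function is not analysed at all, and the protocol does not support that. What remains is that renal function is the one clinical outcome given its own named analysis, and that analysis estimates an overall effect. At best there are two competing analyses for one endpoint.

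A reader might also infer that the plan deletes incomplete patients, about 26 of 100 at 5% missing per visit. The protocol sets no complete-case rule, and base R keeps them. Section 5 also asks voluntary withdrawers to continue scheduled evaluations, laboratory values are daily on days 0 to 7, and section 4.2 takes only controls still on follow-up. Losses may therefore be smaller. The poor fit of the model to incomplete series stands either way.

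A third tempting reading is that the protocol treats these data as skewed and then contradicts itself with a normal-theory model. It never says they are skewed. Medians and Mann-Whitney tests are only its general rule, and the group test is robust at this size.

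For dose and concentration-to-dose ratio, the endpoints are themselves averages over 90 days, so an overall effect is not off target there. Finally, an unseen SAP may settle missing data and covariance structure. The choice of model, however, is fixed in the protocol.

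**Conclusion.** The point holds for two things: the mismatch between an overall renal effect and a month-3 endpoint, and a model poorly suited to series that the protocol itself expects to be incomplete. The mismatch rests on the text and is the stronger of the two. Its arithmetic (3 mL/min from an early difference alone, dilution to one fifth for a month-3-only effect) needs only complete data with five equally weighted visits. The test probabilities rest on the assumed 50 per group, correlation and effect patterns. The share of patients lost is conditional on complete-case analysis and independent gaps.

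The matter should be corrected but is not critical. The endpoints are secondary, the study is a pilot, and the day-3 chi-square comparison is untouched.

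**What to change.** In section 8.2, replace the between-within ANOVA with a linear mixed model on all available values, with a patient random effect or unstructured covariance and with visit, factor and factor-by-visit terms. Name the factor for each outcome:

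- **Tacrolimus daily dose, trough and dose-adjusted level:** CYP3A5 genotype, as now planned.
- **eGFR:** dosing approach. Report the day-90 contrast with its 95% CI as the estimate for the renal endpoint, and the overall effect as supportive.

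Analysing the tacrolimus variables on the log scale and reporting ratios is optional. It brings a modest gain in power and interpretability and does not correct an error. The mixed model uses the values that exist. It cannot supply tacrolimus doses or levels after a patient has left the drug.

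The cost is protocol or SAP wording and slightly more analysis work. R can fit the model, and no new data are needed.
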